3.1.2 *Study Methodology*

Participants will be screened in the period Day -42 to Day -1. Informed consent will be obtained before any study specific procedures are performed. Eligible participants will then attend the clinic to receive study vaccine on Day 0. Participants will be enrolled sequentially.

The study will investigate response to study vaccine as shown in [Table 2](#). On Day 0, an electronic diary (eDiary), tape measure and thermometer will be provided to perform self-assessment of local and systemic reactogenicity. All participants will then have a follow-up telephone call on Day 1 and return to the clinic for study assessments on Days 7, 14, 28, 84. Participants in cohorts 1-4 only, will also have follow up visits on Day 56 and Day 168. End of study visit procedures will be performed at the final visit.

Five healthy participants will be administered the low dose first (cohort 1). Dose escalation will only be initiated in the next 5 healthy participants (cohort 2) following SMC review.

Six CHB participants will be administered the low dose (cohort 3) before the dose escalation is initiated in the remaining 6 CHB participants (cohort 4).

Thirty healthy participants (15 who have received two doses of AZD1222 [cohort 5] and 15 who have received at least two doses of either Pfizer or Moderna mRNA COVID-19 vaccine [cohort 6]) will be dosed in parallel with the high dose used in cohorts 2 and 4.

The first participant in each of cohorts 1-4 will be assessed for 1 hour in the clinic post-vaccination in case of immediate adverse events (timed after the end of study vaccine administration). All other participants will be assessed for 30 minutes.

The safety and immunogenicity assessments to be performed in cohorts 1-4 are:

- Haematology (full blood count, haemoglobin, haematocrit, erythrocytes, mean cell volume, mean corpuscular haemoglobin, mean corpuscular haemoglobin concentration, leukocytes, neutrophils, lymphocytes, monocytes, eosinophils, basophils, fibrinogen, prothrombin time [PT] and international normalised ratio [INR], activated partial thromboplastin time [aPTT] and platelets) will be analysed at screening, pre-vaccination on Day 0 and on Days 7, 14, 28, 56, 84 and 168
- Biochemistry (sodium, potassium, urea, creatinine and albumin) will be analysed at screening, pre-vaccination on Day 0 and on Days 7, 14, 28, 56, 84 and 168

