- Liver function tests (LFTs; alkaline phosphatase [ALP], gamma-glutamyl transpeptidase [GGT], alanine transaminase [ALT], aspartate transaminase [AST] and

total bilirubin) will be analysed at screening, pre-vaccination on Day 0 and on Days 7, 14, 28, 56, 84 and 168

- HBV disease markers in serum:
 - Healthy participants: qualitative HBsAg will be tested at screening, hepatitis B surface antibody (HBsAb) and HBcAb will be tested at Day 0, and repeated at the end of the trial if negative at baseline, or at discretion of the Investigator
 - CHB participants: HBV DNA and quantitative HBsAg will be tested at screening and repeated on Days 0, 28, 56, 84 and 168. The following parameters will also be analysed on days 0, 28, 56, 84 and 168: HBeAg, HBcAg, anti-HBs, anti-HBe, anti-HBc, pgRNA
- A full physical examination will be performed at screening and pre-vaccination on Day 0. A symptom-directed physical examination will be performed on Days 7, 14, 28, 56, 84 and 168
- Vital signs will be performed at screening, pre-vaccination and post-vaccination at the on Day 0 and on Days 7, 14, 28, 56, 84 and 168
- Local and systemic reactogenicity (pain, induration, warmth, erythema at the vaccination site plus feverishness, chills, myalgia, fatigue, headache, nausea, arthralgia, malaise) will be captured pre-vaccination and post-vaccination on Day 0 and by eDiary for 3 days post-vaccination
- Unsolicited adverse events will be recorded in the eCRF from the date the informed consent is signed, at all clinic visits to cover the period since the previous visit and during the visit and up to 28 days post-vaccination
- Serious adverse events (SAEs) and adverse events of special interest (AESIs) will be recorded from the date the informed consent is signed until the end of the study and or resolved or until participant contact discontinues
- Cellular immune responses will be measured in peripheral blood mononuclear cells (PBMCs) samples taken on pre-vaccination on Day 0 and on Days 14, 28, 56, 84 and 168. Samples will be analysed by ICS

For participants in cohorts 5 and 6, all assessments on Days 0, 7, 14, 28 and 84 above will be performed. In addition, neutralising antibodies to ChadOx1 will be assessed on Days 0 and 84.

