3.1.3 Study Stopping Criteria/Holding Criteria/Dose Escalation Process

There will be a review of the study data by the DMC when there is a reasonable possibility that the investigational vaccine caused any of the listed following adverse events based on the assessment of the Investigator in one or more participants at any dose. Vaccinations will be held pending this review:

- Death
- Life-threatening adverse event or life-threatening suspected reaction
- Serious suspected adverse reaction

- Suspected, unexpected, serious adverse reaction (SUSAR)
- Acute allergic reaction or anaphylactic shock following the administration of vaccine investigational product
- Anaphylaxis or bronchospasm, indicative of an immediate hypersensitivity reaction to study vaccine
- If any participant has any of the following:
 - ALT or AST >8 x upper limit of normal (ULN)
 - ALT or AST >5 x ULN for more than 2 weeks
 - ALT or AST >3 x ULN and (total bilirubin >2 x ULN or INR >1.5)
 - ALT or AST >3 x ULN with the appearance of fatigue, nausea, vomiting, right upper quadrant pain or tenderness, fever, rash, and/or eosinophilia (>5%)

The competent authority and Research Ethics Committee (REC) will be notified of a temporary halt within 15 days according to the local requirements. If, following the review of data, a recommendation is made by the DMC to resume study enrolment and vaccine administration, the DMC will record their judgment in a memorandum to the study file and notify the Sponsor. The DMC memorandum will be forwarded to the local Medical Monitor and Investigators.

3.1.4 *Duration of Study*

3.1.4.1 *Duration for Each Participant*

Cohorts 1-4: Up to 8 months (up to 1.5 months for screening and 6.5 months on the study with study vaccine given on Day 0).

Cohorts 5 and 6: Up to 4.5 months (up to 1.5 months for screening and 3 months on the study with study vaccine given on Day 0).

3.1.4.2 *Duration of Study*

It is planned that the study will take 16 months to implement, enrol and read out.

The end of the study is defined as the date of database lock.

3.2 *Discussion of Study Design*

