6 STUDY PROCEDURES AT EACH VISIT/SCHEDULE OF ASSESSMENTS

The study consists of the following:

- A 42-day screening period before the start of the study period
- A study period of 168 days, consisting of a vaccination day on Day 0, a follow-up telephone call on Day 1 and follow-up visits on Days 7, 14, 28, 56. Participants in cohorts 1-4 only, will also have follow up visits on Day 56 and Day 168. End of study visit procedures will be performed at the final visit.

The schedule of assessments at each visit is shown in [Table 2](#) and listed in [Section 6.1](#) to [Section 6.4](#). The study assessments are described in [Section 7](#).

Note: any additional visits or assessments performed during the study e.g. to assess adverse events must also be recorded on the unscheduled procedures or unscheduled visits in the eCRF.

Table 2 Overall Schedule of Assessments at Each Study Visit

Visit/Call	Screen	Vaccination			Follow-up						End of Study	
	Timepoint	Day -42 to -1		Day 0	Day 1	Day 7±1	Day 14±1	Day 28±2	Day 56±3 (cohorts 1-4)	Day 84±7[a]		
		Pre-	0	Post-								
Informed consent		X										
Baseline/eligibility variables												
Demographics		X										
Inclusion and exclusion criteria		X	X									
Height and Weight		X										
Medical and disease history		X	X									
HIV Ab, HCV Ab, HBsAg, HDV Ab[b]		X										
Urinalysis		X										
Urine pregnancy test (β -hCG) [c]		X	X						X	X	X	
Laboratory eligibility and safety tests												
Haematology [d]		X	X			X	X	X	X	X	X	
Biochemistry[d]		X	X			X	X	X	X	X	X	
Liver function tests[e]		X	X			X	X	X	X	X	X	
Study vaccination												
Vaccination				X								
Post-vaccination observation[f]					X							
Other Safety assessments												
Full physical examination		X	X									
Directed physical examination if required						X	X	X	X	X	X	
Vital signs[g]		X	X		X		X	X	X	X	X	
Local/systemic reactogenicity [h]			X		X	X						
Unsolicited adverse events [i]		X	X	X	X	X	X	X				
Serious adverse events and adverse events of special interest		X	X	X	X	X	X	X	X	X	X	
Prior and concomitant medications		X	X	X	X	X	X	X	X	X	X	
Blood for HBV disease markers												
Healthy participants (HBsAb, HBcAb)			X								X[j]	
CHB (HBV DNA, HBsAg quantitative)		X	X						X	X	X	

Visit/Call	Screen	Vaccination			Follow-up						End of Study	
		Day -42 to -1		Day 0		Day 1	Day 7±1	Day 14±1	Day 28±2	Day 56±3 (cohorts 1-4)	Day 84±7[a]	
		Pre-	0	Post-								
CHB (HBeAg, anti-HBe, anti-HBs, pgRNA, HBcAg, anti-HBc)		X							X	X	X	X

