Immunogenicity assessments												
Blood for cellular immunogenicity [k]		X						X	X	X	X	X
Blood for neutralising antibodies (cohorts 5 and 6 only)			X								X	
Liver fine needle aspirates[l]†	X										X	

Abbreviations: ALP=alkaline phosphatase; ALT=alanine transaminase; aPTT=activated partial thromboplastin time; AST=aspartate transaminase; CHB=chronic hepatitis B virus; DNA=desoxyribonucleic acid; GGT=gamma-glutamyl transpeptidase; HBcAb=hepatitis B core antibody; HBsAb=hepatitis B surface antibody; β-hCG=beta human chorionic gonadotrophin; HBcAg=hepatitis B core-related antigen; HBV=hepatitis B virus; HBeAg=hepatitis B e antigen; HBsAg=hepatitis B surface antigen; HCV=Hepatitis C virus; HDV=Hepatitis D virus; HIV=human immunodeficiency virus; ICS=intracellular cytokine staining; INR= international normalised ratio; LFNA=liver fine needle aspirate; pgRNA=pre-genomic RNA; PBMCs=peripheral blood mononuclear cells; PT=prothrombin time

†Optional assessments

- [a] End of Study Visit for cohorts 5 and 6
- [b] HDV Ab serology and HBsAg quantitative test will be done in CHB participants only; HBsAg qualitative test will be done in healthy participants; all participants will be tested for HIV and HCV serology
- [c] Female participants only
- [d] Full haematology (including PT/INR and aPTT) and biochemistry panel
- [e] Measurement of ALP, GGT, ALT, AST and total bilirubin
- [f] The first participant in each cohort will be assessed for 1 hour in case of immediate adverse events (timed after the end of study vaccine administration). All other participants will be assessed for 30 minutes
- [g] Pulse, blood pressure and temperature
- [h] Captured during clinic visits and then via eDiary for 3 days post-vaccination
- [i] Recorded in the eCRF from the date the informed consent is signed, at all clinic visits to cover the period since the previous visit and during the visit and up to 28 days post-vaccination
- [j] If negative at baseline, at discretion of the investigator
- [k] To be processed into PBMCs for analysis by ICS
- [l] Only in CHB participants who consent to LFNA after confirming eligibility. Coagulation profile must be assessed prior to repeat LFNA on Day 84. For those consenting to LFNA, blood for PT/INR and aPTT testing must be collected

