6.1 Screening and Baseline Pre-Dose Assessments

Written informed consent for participation in the study must be obtained before performing any study specific screening tests or evaluations according to the process in [Section 13.4](#).

Unsolicited adverse events will be recorded from the date the informed consent is signed and at all clinic visits up to 28 days post-vaccination, by questioning the participant at each visit whether they had any adverse events since the previous visit and by observing the participant during clinic visits.

Serious adverse events and AESIs will be recorded from the date the informed consent is signed until the end of the study and/or resolved or until participant contact discontinues.

The following will be performed at screening:

- Demographic data will be collected
- Height and weight will be measured
- A medical and disease history will be recorded, including any medications being taken
- A blood sample will be taken for HIV, HCV, HBV, and in CHB participants only, hepatitis D Virus (HDV) diagnostic testing
- Blood samples will be taken for haematology (including PT/INR and aPTT), biochemistry and LFTs
- A urinalysis dipstick test will be performed
- A urine pregnancy test will be performed, childbearing status recorded and if of childbearing potential, assessment of contraceptive measures performed
- A full physical examination will be performed
- Vital signs (pulse rate, blood pressure and temperature) will be measured

All screening evaluations must be completed and reviewed to confirm that participants meet all eligibility criteria before the first dose of study vaccine. The Investigator will maintain a screening log to record details of all participants screened and to confirm eligibility or record reasons for screening failure, as applicable.

Concomitant medications will be recorded throughout the study by questioning the participant at each visit whether they took any concomitant medications since the previous visit.

In CHB participants who consent to LFNAs: a LFNA will be performed within the screening period, after screening tests have shown eligibility, as directed by the Principal Investigator or delegated physician. These aspirates and subsequent assessments are optional

NB. Coagulation profile must be assessed prior to repeat LFNA

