The reporting period for all adverse events begins on the date the informed consent is signed. Solicited adverse events are recorded in the eDiary up to 3 days post-vaccination. All other events are recorded in the eCRF up until Day 28. All SAEs and or Adverse events of special interest are recorded until at least 168 days after the last study vaccination dose and for all serious or study vaccine-related adverse events until these are resolved or until participant contact discontinues.

Adverse event information will be collected at study visits and participant will be instructed to call study team members to report any abnormalities during the intervals between study visits and to come to the study centre if medical evaluation is needed and the urgency of the situation permits.

8.2.3 *Recording and Assessment of Adverse Events by the Investigator*

Solicited adverse events are recorded in the eDiary up to 3 days post-vaccination. All other adverse events are recorded in the eCRF up to until Day 28. All adverse events, both those observed by study team members and those spontaneously reported by the participant, will be recorded in the eCRF. Solicited adverse events will be reported using pre-defined terms. Unsolicited adverse events will be reported using a recognised medical term or diagnosis that accurately reflects the event.

Adverse events will be assessed by the Investigator, or a medically qualified study team member, for severity, relationship to study vaccine, action taken, outcome and whether the event meets criteria as an SAE according to the following guidelines:

8.2.3.1 *Assessment of Severity*

The severity of adverse events will be graded according to the toxicity table in [Appendix 1](#). The scale shown in [Table 3](#) will be used to assess severity of adverse events not listed in [Appendix 1](#).

Table 3 Severity Grading of Adverse Events not listed in the Toxicity Table for Clinical and Laboratory Abnormalities

Grade	Severity	
1	Mild	Asymptomatic or mild symptoms; clinical or diagnostic observations only; or intervention not indicated; no disruption of normal daily activity.
2	Moderate	Minimal, local, or non-invasive intervention indicated; discomfort sufficient to reduce or affect daily activity.
3	Severe	Severe or medically significant, but not immediately life-threatening; hospitalisation or prolongation of hospitalisation indicated; inability to work or perform normal daily activity.

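### Protocol 8.2.2 sets a 168-day minimum for recording SAEs and AESIs in all participants, but cohorts 5 and 6 (30 of 52) have no scheduled contact after Day 84, and SAP Table 14.1.1 gives them the wrong completion day

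*Protocol*

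**What the plan says.** **The minimum.** Protocol 8.2.2 reads: "All SAEs and or Adverse events of special interest are recorded until at least 168 days after the last study vaccination dose". The sentence goes on to carry serious or vaccine-related events forward until they resolve or contact with the participant ends. The same section says that information comes from study visits and from participants telephoning the site between visits.

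**The schedule.** Protocol 3.1.2 says: "Participants in cohorts 1-4 only, will also have follow up visits on Day 56 and Day 168". Footnote [a] to Table 2 marks the Day 84 (+/- 7) column as "End of Study Visit for cohorts 5 and 6". Protocol 3.1.4.1 gives the time on study: "Cohorts 5 and 6: Up to 4.5 months (up to 1.5 months for screening and 3 months on the study".

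**Other statements of the recording period.** Protocol 3.1.2 says that SAEs and AESIs "will be recorded from the date the informed consent is signed until the end of the study and or resolved", and adds the end of participant contact as a further stopping point. Protocol 6.1 has the same rule: "Serious adverse events and AESIs will be recorded from the date the informed consent is signed until the end of the study". Protocol 3.1.4.2 defines that end: "The end of the study is defined as the date of database lock". Protocol 8.2.4 has SAEs reported throughout the study period, which Section 6 describes as "A study period of 168 days, consisting of a vaccination day on Day 0", and 8.2.4.2 asks for attempted follow-up of every participant to the end of the study.

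**The SAP.** SAP 10.1.1 defines completion as Day 168 (+/- 7) for cohorts 1 to 4 and Day 84 (+/- 7) for cohorts 5 and 6. Footnote [5] of Table 14.1.1, a table that includes columns for cohorts 5 and 6, gives Day 168 (+/- 7) only. The adverse event tables take percentages on the safety analysis set, include a Total column and state no length of follow-up.

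**The concern.** SAE incidence is one of the primary endpoints. A reader who goes by 8.2.2 would assume that an absence of SAEs or AESIs in cohorts 5 and 6 reflects at least 168 days of recording. Scheduled enquiry supports about 84 of those days. The rest depends on someone contacting the site.

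The routes left after the final visit are narrow. Protocol 8.2.6 asks participants for later events that their physician thinks related, and asks the investigator to pass on events believed related. An SAE counts whatever its cause, so unrelated SAEs and AESIs are the most likely to be missed. Protocol 8.5.1 covers pregnancies within 6 months of dosing, but that adds little here.

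The Table 14.1.1 footnote is a separate, simpler error. Applied literally, no participant in cohort 5 or 6 could be counted as having completed the study.

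**Working it through.** **Inputs.** Cohort sizes are 5, 5, 6, 6, 15 and 15 (SAP Table 1; Protocol Table 1 and 3.1.2). The last scheduled contact is Day 168 in cohorts 1-4 and Day 84 (+/- 7) in cohorts 5 and 6 (Protocol Table 2). The stated minimum is 168 days (Protocol 8.2.2).

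**Planned total.** 5 + 5 + 6 + 6 + 15 + 15 = 52, which matches the protocol.

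**Participants affected.** 15 + 15 = 30, and 30/52 = 57.7%. Among high-dose recipients (5 + 6 + 15 + 15 = 41), 30 (73%) have their last scheduled contact at Day 84, and 11 are scheduled to Day 168.

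**Scheduled coverage against the 8.2.2 minimum** (participants x last scheduled day):

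| Last cohort 5/6 visit | Scheduled person-days | Implied by 8.2.2 | Share | Unscheduled |
|---|---|---|---|---|
| Day 77 | 22x168 + 30x77 = 6,006 | 52x168 = 8,736 | 69% | 2,730 |
| Day 84 | 22x168 + 30x84 = 6,216 | 8,736 | 71% | 2,520 |
| Day 91 | 22x168 + 30x91 = 6,426 | 8,736 | 74% | 2,310 |

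Unscheduled does not mean uncaptured. These figures only describe the schedule, since the SAP plans no person-time analysis.

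**Possible effect on the Total column (assumed inputs).** The documents give neither an SAE rate nor a capture rate after Day 84. Let p be the 168-day risk of an SAE, with a constant rate, and let c be the fraction of late first events that the site still learns of. The 84-day risk is q = 1 - sqrt(1 - p), and the expected shortfall is 30 x (1 - c) x (p - q) participants.

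| Assumed p | q | Shortfall, c = 0 | c = 0.5 | c = 1 |
|---|---|---|---|---|
| 1% | 0.501% | 0.15 | 0.07 | 0 |
| 2% | 1.005% | 0.30 | 0.15 | 0 |
| 5% | 2.532% | 0.74 | 0.37 | 0 |
| 10% | 5.132% | 1.46 | 0.73 | 0 |

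If 90% of the risk instead falls before Day 84, the c = 0 figure is 30 x 0.1 x p, which is 0.03 to 0.30 participants over the same range of p.

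**Completion rule.** SAP 10.1.1 has two days, by cohort. Table 14.1.1 footnote [5] has one. Protocol Table 2 and 3.1.4.1 agree with SAP 10.1.1, so the footnote is the text to change.

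**The case against.** The best defence is that 8.2.2 promises recording, not scheduled contact. A duty to record can outlast the visit schedule, and Table 2 shows that schedule openly. Sections 3.1.2, 6.1, 8.2.4 and 8.2.4.2 keep the duty alive, and the end of the study is database lock rather than a participant's last visit. This stands, and it limits the point to how events would be found.

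The clause on contact ending does not remove the difficulty. In 3.1.2 and 6.1 it plainly qualifies SAE and AESI recording. In 8.2.2 its reach is arguable, because it follows the words on serious or related events. If it does qualify the minimum, a site could treat Day 84 as closing collection in cohorts 5 and 6, and the 168-day figure would then have little force for them.

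Two stronger readings are tempting. A reader might infer that SAEs after Day 84 in cohorts 5 and 6 go uncollected, so that their SAE counts are biased. The documents do not support this: the recording and follow-up provisions above continue, and nothing says how many late events a site would hear of. A reader might also infer from the Version 7.0 change list, which added these cohorts without naming 8.2.2, that the sentence was overlooked. Deliberate retention of the minimum fits that list equally well.

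It is also fair to say that the SAP consequences are slight. The split is stated in its text (Section 6 and 10.1.1), and the footnote error affects a disposition table, not a safety result.

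**Conclusion.** The point holds as a minor inconsistency. Protocol 8.2.2 sets a 168-day minimum for everyone, and the schedule gives 30 of 52 participants no planned contact in the second half of that period. Table 14.1.1 footnote [5] is wrong against SAP 10.1.1.

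The consequence is small. The analysis is descriptive, each cohort has its own column, events are dated in Table 14.3.2.1 and Listing 16.2.7, and completion dates are in Listing 16.2.1.1. Non-serious unsolicited events (to Day 28) and solicited reactions (3 days) are unaffected. What remains is the unlabelled pooling in Total and comparisons of cohort 2 with cohorts 5 and 6, which have different scheduled follow-up.

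The counts and the conflict between sections come straight from the documents. The shortfall figures rest on assumed risks of 1% to 10% and assumed capture; they show scale and do not predict a loss.

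**What to change.** 1. **Protocol.** Keep the 168-day minimum in 8.2.2 and its clause on following events until resolved. Add one safety telephone call at Day 168 (+/- 7) for SAEs and AESIs in cohorts 5 and 6, and update 3.1.2, 3.1.4.1, Section 6 and Table 2. If no call is added, state in 8.2.2 that collection in these cohorts is active to the Day 84 visit, and that any SAE or AESI the site learns of is still recorded to at least Day 168 and followed until resolved. The Day 168 minimum should not be replaced by the end of the study: that is database lock, for which no date is given, and it could fall before Day 168 for a late participant.
2. **SAP Table 14.1.1.** Correct footnote [5] to Day 168 (+/- 7) for cohorts 1-4 and Day 84 (+/- 7) for cohorts 5 and 6, as in SAP 10.1.1.
3. **SAP Tables 14.3.1.1 and 14.3.1.3, if no call is added.** Footnote the SAE and AESI rows to say that scheduled follow-up is 168 days in cohorts 1-4 and 84 days in cohorts 5 and 6, and that Total combines both.

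**Cost.** The call means one contact for each of 30 participants, a longer time on study than the three months in 3.1.4.1, and a protocol amendment that may need approval under Protocol 13.5. The wording alternative also needs an amendment but no extra contact; its price is openly stating the shorter active collection. The footnotes cost almost nothing. If these cohorts have already passed Day 168, the call is no longer possible; items 2 and 3 still apply, and the clinical study report can describe the difference.
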